3.3. Masking

The clinical professionals hired by the project who assess patients during follow-up, statisticians, and study sponsors will be kept unaware of the treatment assignments. Masking of participating patients will be carried out by providing an informative brochure on bronchial

asthma, given as part of the standard education when explaining the disease. These informative brochures will be crafted using everyday language in Spanish, without incorporating pictograms into their content.

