2.1 Clinical Trial Description

In order to determine the effects of implementing a pictogram platform to facilitate understanding and therapeutic adherence, a randomized parallel-group, triple-masked clinical trial will be conducted with patients recently diagnosed with asthma (≤ 15 days) who enter the Asthma respiratory Units (ARU), hereinafter referred to as ARU, at the Family Health Centers (CESFAM) belonging to the Municipal Health Corporations of the cities of Valparaíso, San Antonio, Hualpén, and Talcahuano. This protocol has been drafted in accordance with the 2010 CONSORT statement (CONSORT 2010).

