2.3.2 Assignment to intervention group A or control group B

- Patients will be randomized using a permuted block method to receive one of two possible intervention strategies A or B.
- The permuted block technique aims to ensure a periodic balance in the number of subjects assigned to each intervention or control group (Molina et al., 2015).
- The random assignment sequence will be generated by technical staff of the project with the support of a statistician.

Intervention Group A: This intervention involves utilizing a pictogram system named SIMAP (Automatic Association System of Medical Instructions to Pictograms), which was developed during the initial phase of the study. In essence, SIMAP comprises a series of pictograms intended to enhance the understanding of medical instructions provided by the healthcare team regarding asthma management. The pictograms will be designed by a panel of experts, as detailed in the previous sections of the project, and validated among adult patients consulting in the same population where this study will be implemented. The designed pictograms are specifically tailored to certain elements within the management of bronchial asthma.

This intervention entails furnishing the patient with the instruction sheet given by the clinical staff of the CESFAM as part of their care, but supplemented with pictograms (automatically generated by SIMAP). The provided instructions include images supporting guidance for recognizing bronchodilators, indicating their method of use (daily dose, usage schedule, or as needed), specifications of bronchodilator families with their functions (disease-controlling and symptom-relieving drugs), inhalation technique of bronchodilators, and the use of an inhalation chamber in the process.

The pictograms will be administered by the clinical professional of the CESFAM designated by the Director or by the clinical professional hired by the project (recruiter). This depends on the care process of the CESFAM participating in this study and the availability of hours of the clinical professional of the CESFAM designated by the Director to support the project.

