Control Group B: This corresponds to those patients selected and who agreed to participate in the study but will not be assigned to receive the SIMAP system (control group) through the randomization method. These patients will receive their medical instructions in the usual manner, as established by the healthcare team of the participating clinics. Additionally, these patients will receive an informative brochure on bronchial asthma, provided as part of the

standard education when explaining the disease. These brochures will be crafted using everyday language in Spanish, without incorporating pictograms into their content.

The research team will not intervene in any way in the selection of bronchodilators by the healthcare team or in any other decision-making regarding the management of bronchial asthma among participating patients.

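### The plan calls patients masked by a text brochure, but nothing described hides the pictograms from them, so the patient-answered ACT should not be presented as masked to the material received

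*Combined protocol and SAP*

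**What the plan says.** Section 2.1 announces "a randomized parallel-group, triple-masked clinical trial will be conducted with patients recently diagnosed with asthma". Section 3.3 names the masked parties. It says that the project clinicians "who assess patients during follow-up, statisticians, and study sponsors will be kept unaware of the treatment assignments". For patients it adds: "Masking of participating patients will be carried out by providing an informative brochure". That brochure contains no pictograms and is described as "given as part of the standard education when explaining the disease".

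Section 2.3.2 describes what each arm receives.

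- Group A: the intervention consists of "furnishing the patient with the instruction sheet given by the clinical staff of the CESFAM as part of their care, but supplemented with pictograms". On delivery it says "The pictograms will be administered by the clinical professional of the CESFAM designated by the Director", or alternatively by the project's recruiter.
- Group B: "These patients will receive their medical instructions in the usual manner, as established by the healthcare team of the participating clinics". It continues: "Additionally, these patients will receive an informative brochure on bronchial asthma, provided as part of the" standard education.

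Table I (section 2.3.4) lists brochure delivery at t0 under Intervention B only. The ACT and the inhalation technique checklist at 7, 30 and 60 days are done by a separate follow-up clinician.

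Section 3.1 makes the ACT at 60 days the primary outcome. The ACT at 7 and 30 days is co-primary, together with inhalation technique. Section 2.3.1 describes the ACT as five questions, each on a 5-point scale.

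**The concern.** Masking a patient to allocation means that the patient cannot tell which intervention was given. Here the intervention is something the patient looks at. A separate text brochure does not change whether the instruction sheet has pictures on it.

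The follow-up clinician may be fully masked, but the ACT score comes from the patient's answers, so assessor masking does not make it a masked outcome. A reader of sections 2.1 and 3.3 would take the primary and co-primary ACT results as coming from patients masked to what they were given. The described design does not have that property. If patients' answers are affected by knowing that they received the illustrated sheet, or that they did not, the ACT difference mixes that effect with any effect on control, and the current text implies that this is excluded.

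The inhalation technique checklist is different, because a masked clinician completes it. That masking is worth stating clearly and protecting.

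A second, smaller matter is the comparison being made. If the brochure goes to Group B only, the A minus B difference compares pictograms with a brochure, each on top of usual instructions. It does not isolate pictograms added to otherwise identical care. A brochure that helps patients would then make the pictogram effect look smaller; it would not create a false benefit.

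**Working it through.** **Step 1: who is masked, and by what.**

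| Party | What the plan says | Described means |
|---|---|---|
| Follow-up assessors | Unaware (3.3) | Separate clinician from recruitment and delivery (Table I) |
| Statisticians, sponsors | Unaware (3.3; for the statistician also 3.4) | Stated; not disputed |
| Patients | Masked (3.3) | Text brochure only |
| Those delivering the material | Not listed as masked | They hand over the sheet or brochure (2.3.2, Table I) |

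For patients, the sheet with pictograms (A) and the usual instructions (B) can be told apart on sight. No section describes a dummy illustrated sheet, another concealment device, or a statement that patients are kept unaware of which material is being tested.

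**Step 2: who receives the brochure.**

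| Place | Reading |
|---|---|
| 2.3.2, Group A | No brochure mentioned |
| 2.3.2, Group B | Given in addition to usual instructions; also called part of standard education |
| Table I | Under Intervention B only |
| 3.3 | Linked to participating patients, no arm named; also called part of standard education |

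The first three agree on B only. Section 3.3 does not say that A receives it, but its wording would fit both arms.

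**Step 3: scale of what the masking claim appears to exclude (illustration only).** The plan has no figure of its own to reproduce here. From the documents: a minimum of 48 patients (3.2), and one response category on one ACT question is 1 point (2.3.1). Assumed: 1:1 allocation, so 48/2 = 24 per arm; ACT SD of 3, 4 or 5; no true effect; two-sided 5% level; a constant average reporting shift s between arms.

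At a single time point with a two-sample t-test, SE = SD × √(2/24), df = 46 and the critical value is 2.013. The 95% half-width is 2.013 × SE, and the rejection rate comes from the noncentral t with noncentrality s/SE.

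| SD | SE | 95% half-width | Rejection, s = 0.5 | Rejection, s = 1 |
|---|---|---|---|---|
| 3 | 0.866 | 1.74 | 8.7% | 20.4% |
| 4 | 1.155 | 2.32 | 7.1% | 13.6% |
| 5 | 1.443 | 2.91 | 6.3% | 10.4% |

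Section 3.4 also names a profile analysis. One reading of it is the Hotelling parallelism test over T0, 7, 30 and 60 days, referred to F(3, 44). Assume equal correlation ρ and a shift of 0 at T0 and s afterwards. The squared deviations of (0, s, s, s) from their mean sum to 0.75s², and 24 × 24/48 = 12, so the noncentrality is 12 × 0.75s²/(SD²(1−ρ)) = 9s²/(SD²(1−ρ)). With s = 1, SD 4 and ρ = 0.5 this is 9/(16 × 0.5) = 1.125, and the rejection rate is 11.8%. For s = 1 and ρ from 0.3 to 0.7 the rates are 14–28%, 10–17% and 8–12% at SD 3, 4 and 5.

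A shift favouring B has the same rates under no true effect, and could hide a real benefit of A.

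**The case against.** The best defence is that section 3.3 uses patient masking in a looser sense. Both arms get something on paper, and a patient who is not told which paper is experimental may not know which arm is the test arm. What patients are told would be in the consent form, which is not in the review copy. This stands in part. It is why the point is limited to what the plan describes, and why a reader should not infer that patients know the hypothesis or that no form of patient masking exists. But being unaware of which material is under test is not being unaware of the material received, and the plan states neither the aim nor the means.

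A second defence is that the brochure assignment is already clear: Group B's description, Table I and the silence for Group A all point the same way. This largely stands. A reader might infer that the comparison is undefined, but the operative text does define one, and section 3.3 only leaves an ambiguity.

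A third is that the false-positive rates rest wholly on an assumed SD, correlation and shift. This stands in full. The documents give no evidence that such a shift will occur, or in which direction.

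Finally, one might make something of the word triple when section 3.3 names four masked parties. That adds little, because the parties are listed.

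**Conclusion.** The patient-masking claim is wrong as written for the material received: the two arms get visibly different instructions and nothing described hides this. The consequence is confined to how the ACT results are described and interpreted. The conclusion follows from comparing sections 2.1, 2.3.2 and 3.3 and does not depend on the illustrative rates.

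Three stronger readings are not supported. The documents do not show that assessor, statistician or sponsor masking fails; no section says, for instance, that patients bring the sheet to follow-up. They do not show that the ACT result will be biased, only that the plan cannot present such bias as excluded. And they do not leave the comparison undefined: as written it is pictograms versus brochure, each on top of usual instructions, with section 3.3 needing clarification.

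The plan should be corrected on this point. The trial can run and be interpreted as masked for assessors, statisticians and sponsors. Confidence is high on the masking claim and lower on the brochure, which is an ambiguity.

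**What to change.** 1. In sections 2.1 and 3.3, replace the general label and the patient-masking sentence with the masked roles: follow-up assessors, statisticians and sponsors. State that patients and those delivering the instructions are not masked to the material received. If patients are kept unaware of which material is under test, say that and how it is done, and claim only that. Describe the ACT as self-report not masked to the material.

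2. Reconcile section 2.3.2 (both groups), Table I and section 3.3 on whether Group A receives the brochure, and describe the comparison to match. The choice is the sponsor's. Giving it to both arms isolates the pictograms but removes any role of the brochure as comparison material. Keeping it in B only preserves that role but does not estimate pictograms added to identical care.

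3. Optional: ask both arms, in the same words, not to mention to the follow-up assessor whether their sheet had pictures. It should go no further, because in Group A the material is the patient's own treatment instructions and the assessor is a clinician checking adherence to recommendations.

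The cost is wording. If the brochure is added to A, about 24 more copies are needed, assuming 1:1 allocation and that A does not already receive it. The downside is a weaker masking claim for the primary outcome. The change does not lower the illustrative error rates; it stops the plan from implying that a reporting shift is excluded.

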3.4. Analysis Strategy

The statistician hired by the project will conduct the data analysis for Stage 2 of the study. Descriptive analysis will initially involve means, standard deviation, absolute and relative frequencies. For inferential analysis, either Student's t-tests or Mann-Whitney tests will be employed to compare means based on the distribution and variances of the obtained data. The Fisher's Exact Test will be used for evaluating qualitative variables.

The primary outcome will be assessed concerning the difference in mean scores observed in bronchial asthma control questionnaires (ACT) between groups at each time point through a profile analysis. The secondary outcome will be evaluated based on the proportion of patients adhering to recommendations regarding the correct use of bronchodilators between both groups. Any intra-group comparisons of qualitative data will be conducted using the ANCOVA or Kruskal-Wallis statistic, depending on the distribution of quantitative data.

All analyses will be carried out by a statistician unaware of the treatment assignment of the participants. Outcomes will be analyzed on an intention-to-treat basis (intervention or control group). In the event of an imbalance in the characteristics of the groups established by the randomization process, potential adjustments to the models will be made. Any model generated will consider the presence of potential interactions between independent variables during its design. Maximum likelihood principles will be ensured based on residual analysis.

To preserve the intention-to-treat principles, missing data will be handled using multiple imputation techniques. All analyses will be performed by a masked statistician using R Project software.

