2.3 Clinical Intervention

2.3.1 Recruitment

A healthcare professional designated by the Director of the CESFAM will be responsible for reviewing the selection criteria for patients entering the ARU during the recruitment period. Upon the first visit (patient's entry into the ARU), if the patient meets the selection criteria, the professional designated by the CESFAM director will introduce the project to the patient and inquire if they would like to meet with the researchers for an invitation to participate in the project by signing the informed consent form. If the patient agrees, the healthcare professional designated by the CESFAM director will inform the project director or a team member designated by her.

Following this, the clinical professional (recruiter) hired by the project will formally invite the patient to participate through the reading and signing of the informed consent. After signing the informed consent, the clinical professional employed by the project (recruiter) will proceed to conduct an interview with the participating patient to obtain a bio-sociodemographic profile, including demographic variables such as gender and age, nationality, time with asthma symptoms, educational level (categorized as basic, middle, higher, and postgraduate education), number of drugs in use, morbidity history as established by the Charlson Comorbidity Index,

smoking history with the corresponding pack-years index, and drugs in use. The initial interview will be conducted by a clinical professional employed by the project. Once the profile is completed, the same clinical professional employed by the project will record the level of disease control at the beginning of the study (time of patient participation acceptance - T0), based on the Asthma Control Test (ACT) questionnaire. This questionnaire has been selected based on its diagnostic capabilities, validation in the Spanish language, and widespread use in both traditional clinical practice and asthma research in Chile. It is currently recommended in national clinical guidelines to establish the level of disease control (Schatz et al., 2006; Vega et al., 2007). ACT scores are established based on 5 questions on a 5-point Likert scale, where higher scores indicate better disease control. Patients with scores above 19 points are considered to have well-controlled asthma.

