3.1. Outcomes

The primary outcome of the study consists of the difference in disease control level 60 days after the start of the study, as assessed by the ACT questionnaire. As co-primary outcomes, the same score difference observed at 7 and 30 days after the intervention has been established, as well as adherence to the recommendations provided by the healthcare team regarding the correct inhalation technique for bronchodilators and the use of inhalation chambers within the same time frames. Secondary outcomes of the study include the recognition of the function of bronchodilators. To check adherence to the correct application of the inhalation technique, the project clinician will conduct an assessment of the correct use of the prescribed inhalation therapy according to a checklist developed 10 months after the start of the project. The checklist was developed following the recommendations of national clinical guidelines, the Spanish Association of Pediatrics in Primary Care, and a study conducted by Santo Tomás University on inhalation techniques in asthmatic patients (Manríquez et al., 2015).ris

Additionally, secondary outcomes will include the occurrence of urgent care visits, hospitalizations related to the disease, and the need to escalate bronchodilator therapy as per GINA guidelines at 60 days. Information regarding these secondary outcomes will be extracted from the individual medical records of each patient, as well as during the final follow-up interview when the ACT questionnaire is administered.

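### Section 3.4 lets the observed data choose between Student's t and Mann-Whitney for comparing means, although Mann-Whitney does not test means when the arms differ in shape or variance

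*Combined protocol and SAP*

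**What the plan says.** Section 3.4 (Analysis Strategy) states for inferential analysis that Student's t-tests or "Mann-Whitney tests will be employed to compare means based on the distribution and variances of the obtained data". It names no diagnostic, no cut-off and no direction of switch.

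The next paragraph of 3.4 assigns the primary outcome to the "difference in mean scores observed in bronchial asthma control questionnaires (ACT) between groups at each time point through a profile analysis". Section 3.1 fixes the primary time point: the "difference in disease control level 60 days after the start of the study, as assessed by the ACT questionnaire", with 7 and 30 days as co-primary.

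On the scale, section 2.3.1 says "ACT scores are established based on 5 questions on a 5-point Likert scale, where higher scores indicate better disease control". It adds that "Patients with scores above 19 points are considered to have well-controlled asthma".

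**The concern.** Mann-Whitney addresses whether a score from one arm tends to exceed a score from the other, that is, whether P(X>Y) + ½P(X=Y) differs from ½. Its reference distribution assumes that the two arms are identically distributed under the null. It speaks to means only if the arms have the same shape. Unequal variance is one of the two features the plan uses to choose the test, and it is a condition under which that equivalence fails.

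The quantity tested would then depend on the data, while the outcome paragraph of 3.4 is about a difference in means. Two things are at stake:

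- A significant Mann-Whitney result could be reported as a difference in mean ACT when only the spread differs.
- Its p-value would not correspond to any reported mean difference and confidence interval.

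An education tool that helps some patients more than others could change spread and shape, so the situation is not far-fetched.

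**Working it through.** **The plan's own figure.** The plan states no error rate for this rule, so there is none to reproduce. The only figure it supplies for the check is the minimum of 48 patients (section 3.2). That is a survey-precision number: 1.96² × 0.25 / 0.10² = 96.04 before a finite-population correction. The population size is not given, so 48 cannot be confirmed. It is used here only as the number randomized.

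**Inputs**

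- From the plan: 48 randomized by permuted blocks (3.2, 2.3.2); the two candidate tests (3.4); five items on 5-point scales and a control threshold above 19 (2.3.1).
- Assumed, because the plan does not say: 1:1 allocation, so 48 / 2 = 24 per arm; two-sided 5% level; items scored 1 to 5, so the scale runs from 5 × 1 = 5 to 5 × 5 = 25.
- Assumed rule: Mann-Whitney if Shapiro-Wilk in either arm, or Levene's test, has p < 0.05; otherwise Student's t.
- Assumed data: discretised beta scores on the integers 5 to 25, with all means and SDs chosen for illustration.

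**Method.** 10,000 simulated trials per setting. The result is the percentage that declare a difference. The simulation standard error is √(0.05 × 0.95 / 10,000) = 0.2 percentage points at 5%, and √(0.188 × 0.812 / 10,000) = 0.4 points at 18.8%.

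**Step 1: both arms share one distribution (no effect on anyone).**

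| Mean, SD in both arms | Mann-Whitney chosen | Rule | Welch |
|---|---|---|---|
| 16, 4 | 17% | 4.7% | 4.7% |
| 20, 4 | 84% | 5.0% | 5.0% |
| 22, 3 | 99% | 4.6% | 5.1% |
| 21, 5 | 100% | 4.9% | 4.9% |

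Mann-Whitney is chosen often, but error stays near 5%.

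**Step 2: equal means, unequal SDs.** Each cell gives the rule / always Mann-Whitney / always Welch, in %.

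| Common mean | SD 3 v 4 (ratio 1.33) | SD 3 v 5 (ratio 1.67) | SD 2 v 4 (ratio 2) |
|---|---|---|---|
| 16 | 4.9 / 5.0 / 4.9 | 5.2 / 5.5 / 5.0 | 5.8 / 5.9 / 5.1 |
| 19 | 5.6 / 5.5 / 5.1 | 8.8 / 8.9 / 5.3 | 7.9 / 8.0 / 5.3 |
| 20 | 6.4 / 6.1 / 4.9 | 12.1 / 12.1 / 5.1 | 10.5 / 10.6 / 5.4 |
| 21 | 7.5 / 7.5 / 5.0 | 18.8 / 18.8 / 5.7 | 14.7 / 14.7 / 5.7 |
| 22 | 10.5 / 10.5 / 5.3 | 29.1 / 29.1 / 6.5 | 26.4 / 26.4 / 6.3 |

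Further runs with other SDs agree: 10–12% at mean 20 with SD 1.9 v 3.9, 12–14% at mean 21 with SD 1.8 v 3.6, and 8–10% at mean 21 with SD 2.2 v 3.3.

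**Step 3: where the excess comes from.** The rule and unconditional Mann-Whitney give almost the same rates, so the preliminary testing adds almost nothing. The cause is the mismatch in what is tested. At mean 21 with SD 3 v 5 the means are equal, yet P(X>Y) with ties counted as half is 0.413, not 0.5. At mean 16 with the same SDs it is 0.491, and there is almost no excess.

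**The case against.** The strongest reply is that in a randomized trial the natural null is that SIMAP affects nobody. Both arms then share one distribution, and the rule holds about 5%. That stands. The frequent choice of Mann-Whitney under identical distributions (17–100% of trials) is not in itself evidence of harm. The excess appears only under a narrower null: equal means, clearly unequal spread, and scores close enough to the ceiling to be skewed. What survives is the mismatch in what is tested, which needs no assumed SD.

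Four stronger readings are tempting, and the documents do not support them:

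- **That the rule doubles or triples the false-positive rate in general, or that a bounded scale alone does so.** The documents give no ACT mean, SD or shape. Mid-scale, or with SDs of 3 v 4 and means up to 21, the rate stays at about 5–8%. The highest values (26–29%) need a mean of 22 and SD ratios of 1.67 or more.
- **That the primary ACT result is affected.** Section 3.4 names a profile analysis for it in a separate paragraph. The t or Mann-Whitney sentence is general, and the plan does not say that it feeds the profile analysis. It does not exclude this either.
- **That the plan prescribes Mann-Whitney when data look non-normal or variances differ.** This is the natural reading, but neither the criteria nor the direction is written.
- **That the Student's t branch is itself a material hazard.** With 24 v 18 analysed, normal data and an SD ratio of 2, Student's t used always gives 7.6%. Under the assumed rule that branch is reached in only 23% of runs, and the rule as a whole gives 6.6%. Such a split also fits poorly with permuted blocks and an intention-to-treat analysis with multiple imputation.

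The masked statistician limits deliberate choice of test, but does not remove the mismatch.

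**Conclusion.** The point holds in a limited form. The wording of 3.4 is wrong: it describes Mann-Whitney as comparing means and lets the observed distribution and variances choose the test, with no criteria, while the stated primary quantity is a difference in mean ACT scores. It also leaves open whether the choice applies to the profile analysis.

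The numerical consequence is conditional:

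- Identical distributions: about 5%.
- Equal means mid-scale: about 5–6%.
- SDs of 3 v 4 with means up to 21: about 5–8%.
- Means of 20–21 with SD ratios of about 1.7–2: about 10–19%, against about 5–6% for Welch.

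Means near 20 are plausible, because the control threshold is above 19 and patients are starting treatment, but the documents do not report them. The figures rest on the assumed 5–25 scale, 24 per arm, a two-sided 5% level, beta-shaped scores and the assumed switching criteria. This should be corrected before analysis. Confidence is moderate.

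**What to change.** Replace the test-selection sentence with one pre-specified analysis that does not depend on the observed distribution:

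- **ACT:** a mean-difference model adjusted for baseline ACT, with heteroscedasticity-robust standard errors, reporting the difference and its 95% CI. State how this relates to the profile analysis, and that no data-driven choice of test applies to either.
- **Other quantitative between-group comparisons:** Welch's t-test.
- **Mann-Whitney:** only as a labelled sensitivity analysis, not described as comparing means.

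The cost is a short change to the SAP wording. Baseline ACT is already recorded at t0 (section 2.3.1 and Table I), and R, which the plan already names, handles these methods. A single model also gives an estimate and standard error that can be pooled across the multiple imputations planned in 3.4; a Mann-Whitney p-value does not supply these. The downside is possibly slightly lower power than a rank test if scores are heavily skewed. The simulations above used unadjusted Welch; the baseline-adjusted robust model was not simulated.

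### Section 3.4 does not commit to using the T0 ACT in the day-60 comparison; always adjusting for it could gain precision at almost no cost

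*Combined protocol and SAP*

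**What the plan says.** Section 3.1 defines the primary outcome as "the difference in disease control level 60 days after the start of the study, as assessed by the ACT questionnaire". It continues: "As co-primary outcomes, the same score difference observed at 7 and 30 days after the intervention has been established".

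Section 2.3.1 provides a baseline value: "the same clinical professional employed by the project will record the level of disease control at the beginning of the study". Table I in section 2.3.4 lists ACT at t0 and again at days 7, 30 and 60.

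Section 3.4 assesses the primary outcome as the "difference in mean scores observed in bronchial asthma control questionnaires (ACT) between groups at each time point through a profile analysis". For comparing means in general it says that "either Student's t-tests or Mann-Whitney tests will be employed to compare means based on the distribution and variances of the obtained data". Its rule on covariates is conditional: "In the event of an imbalance in the characteristics of the groups established by the randomization process, potential adjustments to the models will be made". ANCOVA is named once: "Any intra-group comparisons of qualitative data will be conducted using the ANCOVA or Kruskal-Wallis statistic". The same sentence then makes the choice between the two methods depend on how quantitative data are distributed. On incomplete follow-up, "missing data will be handled using multiple imputation techniques".

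Section 3.2 plans a minimum of 48 patients and says that a calculation from an effect size was not feasible.

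**The concern.** The baseline value of the primary outcome measure is collected from every participant, yet section 3.4 gives it no fixed role in the day-60 comparison. The between-group tests named for means take no covariate. The profile analysis is not described as adjusting for T0. The one sentence naming ANCOVA contradicts itself (qualitative data, but a choice based on quantitative data) and concerns comparisons within groups, so it does not assign ANCOVA to the primary outcome.

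That leaves the imbalance clause. It names no variable, no threshold and no model, and the adjustment is only potential. Whether T0 ACT is used would be settled after the data are seen.

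Precision is at stake. With about 24 patients per arm and no sample size built on an effect, a plan that may leave a prognostic baseline unused can give a wider interval than the same data allow.

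**Working it through.** **Inputs from the documents.** Minimum 48 patients (section 3.2); ACT at t0 and day 60 (Table I); day-60 ACT difference primary (section 3.1). The plan states no power, ACT standard deviation or effect size, so it has no figure of its own to reproduce on this point.

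**Assumptions, not in the documents.** 1:1 allocation (24 per arm), normal scores with equal SD, complete data, two-sided 0.05, day-60 effect 0.8 SD, and T0 to day-60 correlation ρ from 0 to 0.7.

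**Step 1: unadjusted comparison.** The standard error is SD × √(2/24) = 0.289 SD, whatever ρ is. The noncentrality is 0.8/0.289 = 2.77. With 46 degrees of freedom (critical value 2.013) the power is 77%. The 95% CI width is about 2 × 2.013 × 0.289 = 1.16 SD.

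**Step 2: ANCOVA on T0 ACT.** Residual variance falls by the factor 1 − ρ². Estimating the slope raises the variance of the difference by about 1 + 1/44 and costs one degree of freedom (45, critical value 2.014). Hence SE ≈ 0.289 × √(1 − ρ²) × √(1 + 1/44) SD. At ρ = 0.5 this is 0.289 × 0.866 × 1.011 = 0.253 SD, so the noncentrality is 0.8/0.253 = 3.16 and the power is 87%.

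**Step 3: simulation (200,000 trials per cell).** The formulas above agree with it to within about 0.2 percentage points of power.

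| ρ | Power, unadjusted | Power, ANCOVA | Mean CI width, unadjusted (SD) | Mean CI width, ANCOVA (SD) |
|---|---|---|---|---|
| 0 | 77.5% | 76.6% | 1.16 | 1.17 |
| 0.1 | 77.4% | 76.8% | 1.16 | 1.16 |
| 0.3 | 77.4% | 80.2% | 1.16 | 1.12 |
| 0.5 | 77.3% | 87.2% | 1.16 | 1.01 |
| 0.7 | 77.3% | 96.4% | 1.16 | 0.84 |

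The two methods break even near ρ = 0.15. For a 0.5 SD effect, power is about 40% unadjusted at every ρ, and 39%, 39%, 42%, 49% and 65% with ANCOVA.

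**Step 4: adjusting only on imbalance.** The trigger is not stated, so three were assumed, at ρ = 0.5 and 0.8 SD. The full gain is 87.2 − 77.3 = 9.9 points.

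| Assumed trigger on T0 ACT | Fires in | Power | Share of gain recovered |
|---|---|---|---|
| p < 0.05 | 5% of trials | 78.2% | 0.9/9.9, about 9% |
| Difference above 0.3 SD | 30% | 81.3% | 4.0/9.9, about 40% |
| Difference above 0.2 SD | 49% | 83.1% | 5.8/9.9, about 59% |

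None of these rules, fixed in advance, inflates type I error (3.7% to 4.3% at ρ = 0.5). They give up part of the gain, and how much depends on the trigger.

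**The case against.** The strongest reply is that the unadjusted comparison is valid, so baseline adjustment is partly a preference. That stands as far as it goes. The comparison is unbiased, the correlation is unknown, and section 2.2.1 enrols patients who are starting treatment, so T0 ACT may predict day-60 ACT poorly. At a correlation near zero the gain is nil. What remains is an asymmetry: about one point of power at worst against about 10 points at a correlation of 0.5.

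Three stronger readings are tempting, and the documents do not support them.

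- **The primary comparison might be change from T0.** Section 3.4 speaks of mean scores compared between groups at each time point, section 3.1 of a score difference, and neither mentions change from baseline.
- **A global profile test (parallelism or levels) might decide the trial.** Comparison at each time point, with day 60 named as primary, points to the day-60 between-arm contrast. Which test or model delivers that contrast is missing detail, not evidence that a global test would decide.
- **The open choice inflates the false-positive rate.** It would if the analyst computed both the unadjusted and adjusted results and reported the better one: the chance of at least one false positive is then about 6% to 8% for correlations from 0 to 0.7. Nothing in the plan describes that conduct, and the masked statistician limits the scope for it, though masking does not itself fix the analysis.

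**Conclusion.** The point holds as an inexpensive improvement that the plan should adopt. Section 3.4 leaves the role of T0 ACT open and makes adjustment depend on an undefined imbalance. This is not a source of bias.

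The omission is clear from the text. The size of the benefit is less certain: it rests on an assumed effect, an assumed 1:1 split and above all an unknown correlation. The possible gain runs from nothing at low correlation, through about 3 points of power at 0.3, to about 10 at 0.5 and 19 at 0.7. The imbalance-trigger figures illustrate rules the plan does not state. All figures assume complete normal data; multiple imputation was not simulated.

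**What to change.** In section 3.4:

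1. Define the primary estimate as the between-arm difference in day-60 ACT with its 95% CI, from one ANCOVA with arm and T0 ACT. T0 ACT is included whatever balance is observed, and estimates are pooled across the planned imputations.
2. State that this contrast decides the primary outcome.
3. Use the same model form for ACT at days 7 and 30.
4. Remove imbalance-triggered adjustment from the primary analysis.
5. Keep the profile analysis and any Mann-Whitney test as supportive.

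The cost is a few sentences, made before unmasking, and one degree of freedom. No new data are needed, since Table I already has ACT at t0. Under the assumptions above, the downside is about one percentage point of power (77.5% to 76.6%) if T0 and day-60 ACT are uncorrelated.
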